## BOX 2. Typical Counseling Session with a CTTS for Pregnant Women

- Assessment of tobacco use and tobacco use history using an evidence-based tool
- Motivational and practical counseling based on assessment of readiness, including providing education on the maternal and fetal health impacts of smoking
- Provide strong advice to quit as soon as possible
- Exploration of the pros and cons of tobacco use/quitting (decisional balance) and triggers/cues to smoke, including partner smoking and potential engagement in treatment
- Collaboratively developing a tailored treatment plan, which may include but is not limited to incentives, and trigger management strategies, such as stress management or partner support
- Setting a quit date with close follow up
- Discussion relapse prevention strategies during the perinatal and postpartum periods

Our target sample size is 60 participants in each the intervention and control group, for a total of 120 pregnant participants for this pilot project. Additionally, 12 clinic staff and providers will provide quantitative and qualitative data for a mixed-method, multi-stakeholder process evaluation of intervention training and delivery. Due to our limitation of only two participating clinics, we acknowledge that it will not be possible to fully distinguish the effects of the intervention from differences between the two clinic populations. A future larger study of this intervention will include a true group randomized trial, with multiple clinics per treatment, so that the effect of nesting of patients within clinics within treatment will be estimable. In light of this limitation, we will use sample demographic characteristics as covariates in the repeated measures mixed modeling; we acknowledge that the group effects are still likely to be somewhat inflated in this analysis, given the expected artificially small errors due to correlations among patients who visit the same clinic and who may see the same provider. Although we will have limited power, the results from this pilot proof-of-concept study will provide preliminary data to support a highly competitive NIH Health Care Systems Research Pragmatic Trial application.

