### Statistical Analysis Plan

Analysis and estimated power: **Primary outcome:** The primary outcome is smoking cessation in the third trimester, defined as urine cotinine level of <100 ng/mL. **Secondary outcomes** include: self-reported number of cigarettes smoked/day, smoking cessation after delivery, infant birth weight, gestational age at delivery, health care utilization outside of scheduled normal prenatal and infant well-child visits. Two-factor mixed models with group by time interactions will be employed to analyze longitudinal continuous data collected over the course of the trial. Significant main and interaction effects will be explored further using Tukey post-hoc tests. Generalized estimating equation (GEE) modeling will be used to test for significant differences between groups and across time for categorical and dichotomous outcomes; these models will also consider possible group by time interactions. Post-hoc analysis of significant main or interaction effects in the GEE models will be accomplished using contrasts. Demographic and personal factors (e.g., maternal age, gestational age at enrollment) may be included as covariates if linked to outcomes in bivariate analysis. We **hypothesize** that compared with the TTAU group, the ToPIC group will have higher tobacco cessation rates, fewer infants born preterm, and fewer ill child health care visits. While we will assess group differences over time

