in this way, the emphasis on the analysis will be the detection of average differences between the groups, so that we may use this to estimate effect sizes for a larger study in the future. With 60 participants per group and an alpha level of .05, the power of the repeated measures mixed model F test will have at least 90% power to detect a medium effect in the context of group differences, time differences, or a group by time interaction. A medium effect is such that the ratio of the standard deviation of the group means to the standard deviation of the observations within the populations is at least 0.25. While an effect size driven algorithm for estimating the power associated with GEE models has not been developed, logistic regression is considered as a similar technique. With 120 participants and an alpha level of .05, the power of logistic regression to detect an odds ratio as small as 2.3 will be at least 91%. One way to attain an odds ratio of this magnitude would be if the percent of participants in each group with a particular outcome were 50% versus 30%. The power associated with the corresponding GEE model (and extension of logistic regression to the longitudinal application) is expected to be at least as large, given the additional time points included. Power estimates were obtained using nQuery Advisor, v. 6.02 (Elashoff, J. 1995-2005. nQuery Advisor, Statistical Solutions. Saugus, MA).

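### Following a group-by-time interaction in cigarettes per day with Tukey tests spreads the error rate over 15 cell pairs when only three compare the arms at the same visit; same-visit contrasts with Holm adjustment would be better powered (minor)

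*Combined protocol and SAP*

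**What the plan says.** The Statistical Analysis Plan fits a mixed model with arm, time and their interaction to repeatedly measured continuous outcomes, and then states: "Significant main and interaction effects will be explored further using Tukey post-hoc tests". It does not say which means form the Tukey family. Categorical and binary outcomes, including the primary outcome of third-trimester cessation by urine cotinine, go to GEE models, for which it states: "Post-hoc analysis of significant main or interaction effects in the GEE models will be accomplished using contrasts". No adjustment rule is given for those contrasts.

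The same section says that "the emphasis on the analysis will be the detection of average differences between the groups". It claims "at least 90% power to detect a medium effect in the context of group differences, time differences, or a group by time interaction", where a medium effect means that "the ratio of the standard deviation of the group means to the standard deviation of the observations within the populations is at least 0.25".

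Table 1 has four collection points. The tobacco use questionnaire is listed at the last three only (28–34 weeks, and two postpartum visits); baseline has the ACOG screen instead. Urine cotinine and expired-air carbon monoxide are listed at all four.

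**The concern.** Once an interaction is found, the arm effect differs by visit, and the reader wants to know at which visits ToPIC and TTAU differ. An all-pairs Tukey procedure answers that only as a small part of a larger family. Its critical value is set to protect every pair of cell means, including one arm at one visit against the other arm at another visit. The comparisons of interest pay for that protection and gain nothing from it. The text under Box 2 already concedes limited power, so a real visit-specific difference in cigarettes per day could be missed more often than necessary.

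**Working it through.** **Inputs from the documents.** 60 per arm ("Our target sample size is 60 participants in each the intervention and control group"), alpha 0.05, f = 0.25. For two equal arms, f = 0.25 on the group effect is d = 2f = 0.5 SD. Three questionnaire visits, from Table 1.

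**Inputs assumed.** Within-woman correlation ρ is not given and is varied. A difference of 0.5 SD at one visit and none at the others is an assumption, because the plan states no visit-specific effect.

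**1. The plan's own figure.** For the group effect over m = 3 visits, λ = f²·N·m/(1+(m−1)ρ). At ρ = 0.5 this is 0.0625·120·3/2 = 11.25 on 1 and 118 df, giving 91.4% power. The stated 90% is reproduced up to ρ of about 0.55. With only two arms, Tukey on this effect is the ordinary test, so this figure is untouched.

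**2. Counting the pairs.** 2 arms × 3 visits = 6 cells, and 6·5/2 = 15 pairs:
- same visit, different arm: 3
- same arm, different visits: 2·3 = 6
- different arm and different visit: 3·2 = 6

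**3. Critical values.** Tukey uses q(0.95; 6 cells, df)/√2, which is 2.85 for large df and 2.87 at 236 df. That is a per-comparison two-sided alpha of about 0.004. Bonferroni over three uses 2.394; unadjusted is 1.96.

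**4. Power for one same-visit comparison.** The noncentrality is 0.5·√(60/2) = 2.739. Power is Φ(2.739 − critical value), the opposite tail being negligible.

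| Procedure | Critical value | Power |
|---|---|---|
| Unadjusted | 1.96 | 78% |
| Bonferroni over 3 | 2.394 | 63.5% |
| Holm over 3, effect at one visit only | stepwise | 64% |
| Tukey, 6 cells | 2.85–2.90 | 44–46% |

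**5. Requiring a significant interaction first.** This was simulated with 20,000 runs per setting and 60 per arm. The same-visit test counts only if the interaction F test (2 and 236 df) is also significant at 5%.

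| ρ | Tukey | Holm over 3 | Loss, points |
|---|---|---|---|
| 0.3 | 39% | 52% | 13 |
| 0.5 | 42% | 58% | 16 |
| 0.7 | 44% | 62% | 18 |

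These move by about a point with the critical values used.

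**6. Error control.** With no true difference and no gate, the chance of any false between-arm finding is about 1.1–1.3% with Tukey and 3.8–4.7% with Holm at ρ = 0.3–0.7. Both stay within 5%; Tukey leaves most of it unused on these three contrasts.

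**7. Sensitivity.**
- If a continuous outcome is analysed at all four collection points, there are 8 cells, 28 pairs and 4 same-visit pairs. Power is 37–39% with Tukey and 58–60% with Bonferroni over four.
- With an assumed 15–25% loss (51 to 45 per arm), power is 37–32% with Tukey (6 cells) and 55–49% with Bonferroni over three.

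**8. A larger interaction.** A difference d at one of three visits is an interaction of f = d/√18, so d = 0.5 is f = 0.118. An interaction of f = 0.25 carried by one visit needs d = 0.25·√18 = 1.06, where Tukey has 99.8% power. If the effect grows linearly (0, 0.61, 1.22), Tukey has over 99% at the last visit and 69% at the middle one, against 83% with Bonferroni over three.

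**The case against.** The strongest reply is that the reach is small, and that is correct. The primary outcome is binary and goes to GEE. Birth weight and gestational age at delivery are single measurements. Cigarettes per day is the one clearly longitudinal continuous outcome named, and the issue arises only after a significant interaction, in an exploratory step of a pilot. Tukey is also a valid, error-controlling procedure.

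Five stronger readings are tempting, and the documents do not support them.
- **That power is lost on what the plan emphasises.** The emphasis is on the mean arm difference, where Tukey costs nothing.
- **That the alternative has 70% power or more.** That needs an equal effect at every visit, which is no interaction, so the follow-up would be triggered only by chance. Nor is 64% a figure from the plan; it is what the alternative method would give.
- **That 45% is the power at the plan's medium interaction.** A 0.5 SD difference at one visit is a smaller interaction than f = 0.25, as step 8 shows.
- **That the GEE contrasts are unadjusted, so the two model families follow opposite rules.** The SAP is silent on adjustment there.
- **That all 12 other pairs are irrelevant.** Table 1 names cessation or reduction as the outcome at each follow-up, and the plan powers time differences, so the six within-arm changes have some purpose. Only the six cross-arm, cross-visit pairs plainly have none.

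The all-pairs family is itself the conventional reading and not written text. That is a reason to specify it, and does not remove the point.

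**Conclusion.** The point holds in a limited form and is of minor severity. If Tukey is applied to all cell pairs after an interaction in cigarettes per day, a 0.5 SD arm difference at one visit is detected about 45% of the time, against about 64% with Holm over the three same-visit contrasts. With the interaction gate included, the gap is about 13–18 points. This rests on the all-pairs reading, three questionnaire visits, full retention of 60 per arm, an effect confined to one visit, and ρ between 0.3 and 0.7 for the gated figures. The loss shrinks as the interaction grows and nearly vanishes where a single visit carries an interaction of f = 0.25. No conclusion about the primary outcome or the average arm difference is put at risk.

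**What to change.** Replace the Tukey sentence with text to this effect: a significant group-by-time interaction is followed by ToPIC–TTAU contrasts at each of the three follow-up visits, estimated from the mixed model with 95% CIs and Holm adjustment over the three; Tukey tests are used for the time main effect only. A blanket removal of Tukey is not advised, because all-pairs comparison of visits is a sound follow-up to a time main effect.

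State the same three contrasts and the same Holm rule for the interaction follow-up in the GEE models, where no rule is given now. Make clear that this governs the follow-up step and does not redefine the primary third-trimester comparison.

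The cost is a sentence or two in the SAP, with no new data or participants. The downside is that adjusted all-pairs tests of within-arm change are lost from the interaction follow-up; those changes would be described with CIs.

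### The SAP has no rule for a missing cotinine sample: the planned GEE would overstate cessation if continuing smokers are lost more often, and distort the odds ratio if that excess loss differs by arm

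*Combined protocol and SAP*

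**What the plan says.** The Statistical Analysis Plan defines the endpoint: "The primary outcome is smoking cessation in the third trimester, defined as urine cotinine level of <100 ng/mL". Table 1 places that sample at 28-34 weeks, the first collection after baseline. The method for dichotomous outcomes is: "Generalized estimating equation (GEE) modeling will be used to test for significant differences between groups and across time for categorical and dichotomous outcomes". Group-by-time terms are to be considered. Adjustment is optional and depends on association with the outcome, not with loss: "Demographic and personal factors (e.g., maternal age, gestational age at enrollment) may be included as covariates if linked to outcomes in bivariate analysis".

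The protocol and SAP give no expected loss, analysis population, rule for counting a missing cotinine, weighting, imputation or sensitivity analysis. The logistic-regression power statement counts all 120 women as contributing.

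Three design features bear on who might be lost:

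- Under Aim 1, women are told that their urine will be tested at each collection point and that they will learn the result.
- In the paragraphs after Box 1, the CTTS invites ToPIC women to give samples, while a research nurse or key personnel does so in TTAU. Only ToPIC adds counsellor contact at least monthly.
- The two arms are two different clinics (text after Box 2).

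The results are meant to be carried forward: "so that we may use this to estimate effect sizes for a larger study in the future".

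**The concern.** With nothing else specified, GEE is fitted to the visits that were observed. The primary endpoint is a single visit, so a model with group-by-time terms estimates cessation there essentially from the women sampled then. A woman who is still smoking has a reason to avoid a urine test whose result she will be told. The two arms also differ in who asks for the sample and how often she is seen. Loss related to smoking status is therefore plausible, and so is a difference between arms in that loss.

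The pilot's main product is an effect size and a control-arm cessation rate for a larger trial. An error in either goes straight into that trial's sample size. If the rule for missing samples is chosen after the loss is known, the choice can also follow the result.

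**Working it through.** **Inputs from the documents.** 60 women per group; a binary outcome; the SAP's example of 50% v 30%. That example gives an odds ratio of (0.5/0.5)/(0.3/0.7) = 2.33, which agrees with the SAP's 2.3. (The SAP's 91% power does not reproduce for this example: 60 per group gives 61.1%, two-sided. That is a separate point and is not used here.)

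**Inputs that are assumptions.** All loss rates. The documents state none.

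**Formula.** Let p be true cessation in an arm, and rq and rs the proportions of quitters and smokers whose sample is obtained. Then

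- observed rate = p·rq / [p·rq + (1−p)·rs]
- observed OR = true OR × (rq/rs in ToPIC) / (rq/rs in TTAU)

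The second line shows what matters for the odds ratio: not whether smokers are lost more often, but whether the ratio rq/rs differs between arms.

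**Results, with true rates of 50% (ToPIC) v 30% (TTAU):**

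| Assumed loss | ToPIC observed | TTAU observed | OR |
|---|---|---|---|
| (a) Arm only: 10% of ToPIC, 30% of TTAU | 50.0% | 30.0% | 2.33 |
| (b) Both arms: 10% of quitters, 30% of smokers | 0.45/(0.45+0.35) = 56.3% | 0.27/(0.27+0.49) = 35.5% | 2.33 |
| (c) 10% of quitters; smokers 20% ToPIC, 40% TTAU | 0.45/(0.45+0.40) = 52.9% | 0.27/(0.27+0.42) = 39.1% | 1.75 |
| (d) 10% of quitters; smokers 40% ToPIC, 20% TTAU | 0.45/(0.45+0.30) = 60.0% | 0.27/(0.27+0.56) = 32.5% | 3.11 |

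Check by the second formula: (c) 2.33 × (0.9/0.8)/(0.9/0.6) = 2.33 × 0.75 = 1.75; (d) 2.33 × (0.9/0.6)/(0.9/0.8) = 2.33 × 1.33 = 3.11.

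**No true effect (30% in both arms).** Pattern (c) gives 32.5% v 39.1%, OR 0.75. Pattern (d) gives 39.1% v 32.5%, OR 1.33. Either way, a difference of 6.6 points appears from nothing.

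**Check with GEE itself.** A large-sample simulation (40,000 women, three time points, independence and exchangeable working correlation) behaved the same way. Under (b) the OR was 2.27 to 2.34 and the TTAU rate about 35% to 36%. Under (c) the OR was 1.71 to 1.84.

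**Does one simple rule settle it?** Counting missing as not abstinent gives 0.5×0.9 = 45% v 0.3×0.9 = 27% in (b), (c) and (d), so OR = (0.45/0.55)/(0.27/0.73) = 2.21. In (a) it gives 45% v 0.3×0.7 = 21%, so OR = (0.45/0.55)/(0.21/0.79) = 3.08, against a true 2.33. The rule trades one bias for another.

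**Does imputation settle it?** If loss depends on a recorded value such as baseline cotinine, yes: in a check of that case, unimputed ORs of 1.95 to 2.15 returned to about 2.33. If loss depends on current smoking, as in (c) and (d), only in part. With by-arm imputation from a baseline predictor, the 1.75 in (c) moved to about 1.77 when the predictor was weak (log odds ratio 0.5 per SD), and to no more than about 1.95 across the stronger predictors tried. The 3.11 in (d) moved to 3.06 with the weak predictor.

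**The case against.** The strongest reply is that this is silence rather than a wrong method. The SAP does not say that it will analyse available samples only, and GEE can be fitted to weighted or imputed data, or with missing counted as smoking. That stands: the defect is an unspecified rule, and use of observed samples is what follows if none is added.

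Two stronger readings are tempting, and neither is supported. A reader might infer that GEE is valid only if loss is completely random. It also tolerates loss that depends only on covariates in the model, as row (a) shows, so more counsellor contact in ToPIC would cause no bias if it changed retention only by arm. A reader might also infer that the odds ratio is biased whenever smokers are lost more often. Row (b) shows that it is not.

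It is fair to add that Table 1 gives both arms the same samples, time points and payments, and that no passage is evidence of smoker-specific loss differing by arm. Nor would imputation under missing at random cure the scenarios in rows (c) and (d). All participants report tobacco use at entry and the primary sample is the first after baseline, so baseline data may predict little. These points limit the size of the claim and shape the fix. They do not supply the missing rule. The authors' admission that the effect cannot be fully separated from clinic differences concerns another problem.

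**Conclusion.** The point holds in this limited form. The SAP gives no rule for a missing third-trimester cotinine, and the GEE as written is unbiased only if loss is unrelated to smoking status given the model covariates. Excess loss of smokers inflates cessation in both arms (30% seen as 35.5% under the assumed rates). It biases the odds ratio only if the excess differs by arm, and then in either direction (2.33 seen as 1.75 or 3.11). These figures illustrate what could happen under assumed loss rates and are not estimates for this trial. Differential loss is plausible from the design but not shown by it. The change is worth making because the estimate is meant to feed a larger trial and the remedy is cheap.

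**What to change.** Add to the Statistical Analysis Plan:

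1. All enrolled women stay in the denominator for the primary outcome.
2. Missing cotinine is multiply imputed separately by arm, preferably on the log scale, before the GEE is fitted. The imputation uses baseline cotinine, EACO, ACOG screen response, gestational age at enrollment, and any later cotinine, EACO or TUQ value the woman has.
3. A statement that this assumes missing at random and does not by itself remove bias from loss driven by current smoking.
4. Sensitivity analyses: missing counted as not abstinent, and a delta-shift analysis of the imputed values in which the shift may differ by arm. The second is the one that addresses rows (c) and (d).
5. The number and proportion of missing primary samples, reported by arm.

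The trial already plans to collect all the data needed. The cost is SAP wording, a little more analysis and slightly wider confidence intervals.

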### **BOX 1. ACOG's 5A's**

1. **ASK** the patient about smoking status at the 1st prenatal visit and follow-up with her at subsequent visits.
  - A. I have never smoked or I have smoked fewer than 100 cigarettes in my lifetime
  - B. I stopped smoking before I found out I was pregnant and I am not smoking now
  - C. I stopped smoking after I found out I was pregnant, but I am not smoking now
  - D. I smoke now, but I cut down on the number of cigarettes I smoke since I found out I was pregnant
  - E. I smoke regularly now, about the same as before I found out I was pregnant
2. **ADVISE** the patient who smokes to stop by providing advice to quit with information about the risks of continued smoking to the woman, fetus, and newborn.
3. **ASSESS** the patient's willingness to attempt to quit smoking at the time. Quitting advice, assessment, and motivational assistance should be offered at subsequent visits.
4. **ASSIST** the patient willing to make an attempt using counseling and pharmacotherapy to help her quit.
5. **ARRANGE** the follow-up contact, in person or by telephone, preferably within the first week after the quit date.

Usual Care (TTAU): Eligible women randomized to the control group will be informed of the risks of tobacco use and benefits of quitting using the ACOG 5A's approach by their healthcare provider. This standard takes approximately 5-15 minutes, and is offered at each prenatal and postpartum appointment. The research nurse or key personnel will invite participants to complete the tobacco use questionnaires (TUQ), urine cotinine validation, and Expired Air Carbon Monoxide (EACO) analysis to assess ongoing tobacco use at the designated time points; participants will receive a monetary gift card as compensation for their time, at the denominations listed below in Table 1.

The Intervention (ToPIC): Eligible women randomized to the intervention will receive TTAU plus ToPIC administered by the CTTS. At least once monthly, at routinely scheduled prenatal visits or through telephone, the CTTS will provide cessation counseling (see components of a typical counseling session in Box 2). The CTTS will invite participants to complete TUQs, urine cotinine validation and EACO analysis to assess ongoing tobacco use at the designated time points; participants will receive a monetary gift card as compensation for their time. See summary of study procedures in Table 1.

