**Table 1. Summary of Study Procedures**

Time points	ToPIC participants	TTAU participants	Outcome	Compensation
Pregnant Patient Participants:				
Baseline <20 weeks gestation	
 
• Urine cotinine
 
• EACO
 
• ACOG tobacco use screen
 
	
 
• Urine cotinine
 
• EACO
 
• ACOG tobacco use
 
	Eligibility screen for tobacco	\$10
Monthly through end of pregnancy at regularly scheduled prenatal visits	
 
• CTTS tobacco treatment education support, including
 
• Individualized treatment plan (baseline)
 
• 5As
 
• Motivational Interviewing
 
• Navigation to resources
 
	
 
• 5As, as per usual
 
		
28-34 weeks gestation	
 
• Urine cotinine
 
• EACO
 
• TUQ
 
	
 
• Urine cotinine
 
• EACO
 
• TUQ
 
	Tobacco cessation or reduction	\$10
Postpartum 2-8 weeks after delivery	
 
• Urine cotinine
 
• EACO
 
• TUQ
 
	
 
• Urine cotinine
 
• EACO
 
• TUQ
 
	Tobacco cessation or reduction	\$20
Postpartum 12-18 weeks after delivery	
 
• Urine cotinine
 
• EACO
 
• TUQ
 
	
 
• Urine cotinine
 
• EACO
 
• TUQ
 
	Tobacco cessation or reduction	\$20

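### Baseline urine cotinine is collected in both arms but not named as a covariate for the cotinine-defined primary outcome, and the protocol's firm covariate commitment does not reach that outcome's model

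*Combined protocol and SAP*

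**What the plan says.** The Statistical Analysis Plan defines the endpoint: "The primary outcome is smoking cessation in the third trimester, defined as urine cotinine level of <100 ng/mL". Table 1 lists urine cotinine for both arms in the row headed "Baseline <20 weeks gestation", and Aim 1 says urine is tested for cotinine at each data collection point. Eligibility rests on self-reported tobacco use, with no minimum cotinine stated.

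Covariates are mentioned in two places.

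- **Study Protocol, paragraph after Box 2.** Having conceded that two clinics cannot fully separate intervention from clinic, the protocol responds: "we will use sample demographic characteristics as covariates in the repeated measures mixed modeling".
- **Statistical Analysis Plan.** "Demographic and personal factors (e.g., maternal age, gestational age at enrollment) may be included as covariates if linked to outcomes in bivariate analysis".

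The SAP gives mixed models to longitudinal continuous data. For the rest, GEE "modeling will be used to test for significant differences between groups and across time for categorical and dichotomous outcomes". It does not name the primary outcome's model separately. The emphasis is on average group differences, "so that we may use this to estimate effect sizes for a larger study in the future".

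**The concern.** How heavily a woman smokes at enrollment is a natural predictor of whether her cotinine is below a fixed cut-point months later. Because eligibility is by self-report, some women could even be below 100 ng/mL when they enroll. With one clinic per arm, nothing in the design balances smoking intensity between arms. Age and gestational age, the two examples the SAP gives, do not measure it.

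The measurement that could correct this part of the clinic difference is already in hand, but whether it is used is open until outcomes are known. The commitment made because of the two-clinic problem stops short of the primary outcome. If cotinine is left out and the clinics differ, the distortion passes into the effect size used to plan the larger study.

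**Working it through.** **1. The two covariate statements side by side**

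| | Protocol, after Box 2 | Statistical Analysis Plan |
|---|---|---|
| Strength | Committed | Optional |
| Variables | Demographic characteristics | Demographic and personal factors; open list with two examples |
| Condition | None stated | Bivariate link to outcome; no threshold given |
| Models | Repeated measures mixed models | Not restricted |
| Names baseline cotinine? | No | No |

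The primary outcome is dichotomous, so it falls to GEE. Only the right-hand column reaches it.

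**2. The plan's own figure.** The SAP's example of 50% versus 30% gives OR = (0.50/0.50)/(0.30/0.70) = 2.33, agreeing with its 2.3. This is a marginal (unadjusted) odds ratio. The point does not depend on the SAP's power statement.

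**3. Size if cotinine is omitted.** From the documents: 60 women per arm and alpha .05 (two-sided assumed). Assumed, because the documents give no values: no true effect, 30% control cessation, cessation OR of 0.5 or 0.35 per SD of log baseline cotinine, and independent women.

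Model: logit P(cessation) = a + ln(OR per SD) × x, where x is log cotinine in SD units. The control mean of x is 0, the ToPIC mean is shifted, and a is set to give 30% in control. It is a logistic model at one time point, standing in for the GEE, with a Wald test and 20,000 runs per row.

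| ToPIC mean (SD) | OR per SD | ToPIC cessation | Crude OR | Rejects, crude | Rejects, cotinine in model | Rejects, cotinine screened at p<.05 |
|---|---|---|---|---|---|---|
| -0.25 | 0.5 | 33.4% | 1.17 | 6.8% | 5.0% | 4.9% |
| -0.25 | 0.35 | 34.7% | 1.24 | 8.2% | 5.1% | 5.0% |
| -0.5 | 0.5 | 37.0% | 1.37 | 12.0% | 5.1% | 4.9% |
| -0.5 | 0.35 | 39.8% | 1.54 | 20.2% | 5.2% | 4.9% |
| +0.5 | 0.5 | 23.8% | 0.73 | 11.3% | 5.1% | 4.9% |
| +0.5 | 0.35 | 21.6% | 0.64 | 18.1% | 4.9% | 4.7% |

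The model with cotinine also held age and gestational age, simulated as noise. Example of a crude OR: (0.370/0.630)/(0.30/0.70) = 1.37. At 0.1 SD imbalance, crude rejection is about 5-6%, so little is at stake there. When ToPIC was the lighter clinic, the screen kept cotinine in 91-99.8% of runs. Adjusting only for age and gestational age left rejection at 7-21%.

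**4. Scale of the adjusted estimate.** A marginal 50% versus 30% corresponds to a conditional OR of 2.55 (OR per SD 0.5) or 2.81 (0.35), against 2.33 unadjusted.

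**5. What adjustment leaves behind.** With an assumed residual within-clinic ICC and 60 women per clinic, a nominal 5% test rejects with probability 2 × [1 - Φ(1.96/√(1 + 59 × ICC))]:

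- ICC 0.01: 1.96/√1.59 = 1.554, giving 12%
- ICC 0.02: 1.96/√2.18 = 1.327, giving 18%
- ICC 0.05: 1.96/√3.95 = 0.986, giving 32%

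**6. Room in the model.** At 30% cessation and full follow-up, 0.30 × 120 = 36 events. Group plus cotinine is 36/2 = 18 events per term; two further covariates bring it to 36/4 = 9.

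**The case against.** The strongest reply is that the SAP's rule already permits the right analysis. Its list is open, cotinine could be counted as a personal factor, and step 3 shows that a p<.05 screen controls error as well as always adjusting. This stands. The harm arises only if cotinine is never considered, which the documents do not say will happen. What remains is incomplete pre-specification: cotinine is not named, no threshold is given, and inclusion is optional.

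Other objections also have weight:

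- **The size is hypothetical.** Imbalance, strength of association and control rate are all assumed. The return to 5% is partly built in, because the data were generated from the model used to adjust.
- **The larger problem is disclosed and not cured.** The protocol admits the clinic confounding and expects group effects to be inflated, "given the expected artificially small errors due to correlations among patients who visit the same clinic". Step 5 shows that what remains can match or exceed what adjustment removes.
- **The covariate statements need not conflict.** A reader might infer a contradiction. The SAP sentence may instead be the selection step for the protocol's commitment; the text does not settle this, so clarification is what can fairly be asked.
- **Forcing in age and gestational age is not supported.** Nothing calculated here shows a benefit from including them unscreened.

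A reader might also infer that cigarettes per day has no baseline value, since Table 1 lists no tobacco use questionnaire at baseline and the screen records categories such as "I smoke now, but I cut down on the number of cigarettes I smoke since I found out I was pregnant". The questionnaire's content is not given, so the documents do not establish this, and it is not part of the point.

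**Conclusion.** The point holds as a gap in pre-specification. A baseline measurement of the primary outcome's own analyte is collected in both arms and named in neither covariate statement, and the firm commitment made in response to the two-clinic limitation does not extend to the model the primary outcome would use. That the model is GEE is an inference from the outcome being dichotomous.

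The textual omission is certain; the size of the harm is not. Under the assumptions above it is negligible at 0.1 SD clinic imbalance, modest at 0.25 SD, and material at 0.5 SD, where the spurious odds ratio is 1.37-1.54, or 0.73-0.64 in the other direction. The documents do not support saying that the plan excludes cotinine, that its screen is itself the source of error, or that adjustment would make the two-clinic comparison valid. The change is still worth making, because it costs almost nothing and the estimate is meant to inform a larger trial.

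**What to change.** In the Statistical Analysis Plan:

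1. State that the primary GEE, and the later cessation comparisons, adjust for log baseline urine cotinine as a pre-specified covariate. Enter it as a baseline covariate, not as an outcome time point: once dichotomized, the baseline value would be nearly constant among self-reported users and could not replace the continuous measure.
2. State that the protocol's covariate commitment applies to the GEE as well as the mixed models, with any further demographic covariates a short list fixed in advance.
3. Report unadjusted cessation rates and the unadjusted OR beside the adjusted OR, and label the latter conditional, so that the larger trial is planned on a known scale.
4. State that adjustment removes neither other clinic differences nor within-clinic correlation.

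The cost is wording only; no new data are needed. The downsides are one more model term, with about 36 events if cessation is 30%, and an adjusted odds ratio that is not directly comparable with the 50% versus 30% example.
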